It is also University of Rochester policy that all research and clinical staff who may be in contact with protected health information (PHI) demonstrate a working understanding of the University of Rochester's Notification of Health Policies and Practices form. This information form describes to patients and research subjects the University's policies and procedures regarding PHI, consistent with the federal Health Insurance Portability and Accountability Act (HIPAA) and with other relevant university regulations and local, state, and national legislation. All investigators and research staff will complete an information and training session on HIPAA legislation, the University's Notification of Privacy Practices, and on ethical conduct of research in accordance with this legislation and with University regulations.

7. Potential Benefits to the Subjects: All study subjects will receive a behavioral intervention aimed to increase social connectedness and reduce loneliness – an intervention that targets a significant risk factor for reduced well-being, morbidity and mortality. Thus, the potential benefit to the individual may be significant. Subjects may additionally benefit from participating in research interviews and completing the questionnaire measures, as these assessments provide them with the opportunity to be carefully listened to and comprehensively evaluated. They may further benefit from feelings of altruism connected with participation in research designed to better understand the mental health needs and experiences of community-residing older adults.

8. Importance of the Knowledge to be Gained: Importance of the knowledge to be gained from the proposed research: There is a pressing public health need to find interventions that reduce loneliness in later life, which is associated with significant morbidity and mortality among older adults who are caregivers. There are no evidence-based interventions for promoting social connectedness in older adults. Reducing loneliness and promoting connectedness would significantly improve the lives of older adults who are caregivers by improving well-being and promoting health and longevity. Given the minimal risks associated with the proposed research and the substantial gains both to the individual and older adults more broadly, benefits appear to outweigh the risks.

9. Alternatives to Participation: Regarding alternative interventions, subjects will not be prohibited from seeking out supportive social services, or mental health services (for ethical reasons). If subjects do engage these services, he/she will be followed for the full 6 months, with documentation of the nature and extent of that engagement, and evaluation of its impact on the outcomes of interest.

10. ClinicalTrials.gov Requirements: This study will be registered at clinicaltrials.gov

VII. SUBJECT IDENTIFICATION, RECRUITMENT AND CONSENT/ASSENT

1. Method of Subject Identification And Recruitment: Subjects will be recruited via the IRB approved HARP Population Study (RSRB00068059), a research registry run by the current study's Investigators. In compliance with procedures of the Population Study protocol, subjects of the Population Study consent to allow HARP Population Study researchers to share subjects' identifiable data (both name and contact information) with investigators conducting HARP research at the University of Rochester; in addition, they consent to allow their data collected as part of the Population Study to be included in their research record for subsequent HARP studies they participate in, including the current study. All eligible participants will be provided with a study brochure (brochure is uploaded in the rsrb online application). Information about the study will also be posted on the PI's URMC lab webpage (content to be displayed is uploaded in the rsrb online application) and the URMC Clinical Trials website. Information about this study will also be provided in the ResearchMatch registry. We will utilize a REDCap eligibility screening survey given the relatively low base rate of loneliness, which is our key inclusion criteria, to increase the efficiency of our screening/enrollment process. Information about the study will be included at the beginning of the survey. Individuals who complete this survey and endorse loneliness (UCLA Loneliness Scale) and at least mild stress will have the option to provide their contact information to share with the Healthy Aging Research Program (HARP) staff to complete the HARP Database (RSRB00067245) and Population Study (RSRB00068059) assessments, which will provide information needed to determine final eligibility for this Engage Coaching study, which is part of the Rochester Roybal Center for Social Ties & Aging Research. The link to the eligibility screen will be available via research match, the URMC Clinical Trials website, and the URMC website with information about the study.

2. Process of Consent: Consent will be done over the phone or through Zoom. Eligible participants will provide informed consent prior to study start. E-consent will be done through the REDCap module. An agreed upon security question will be used for the subject to access the E-consent. The informed consent process will be conducted in a manner to facilitate questions from potential study subjects. If a study team member is unable to answer a question, an investigator will be contacted. All questions from potential subjects should be answered prior to signature. At the conclusion of the consent process and prior to requesting that they sign the form, all subjects are asked capacity questions prior to signing. Subjects will certify that the information in the document is correct (which includes their name), and that electronically signing is the equivalent of signing a physical document. Subjects will sign using finger, mouse or stylus. The study coordinator's name and timestamp will be saved in REDCap as their signature. Consents will be stored within REDCap, and a copy will be e-mailed to the subject. No subjects will be involved in research activities unless an investigator or a designated study staff has obtained documentation of legally effective informed consent of the subject. The collection of protected health information (PHI) and questionnaires are considered to be research activities requiring prior documentation of informed consent. Consent will only be sought under circumstances that provide the prospective subject sufficient opportunity to consider whether or not to participate and that minimize the possibility of coercion or undue influence. The information that is given to the subject or the representative shall be in language understandable to the subject. Potential study subjects will be given ample time to read and consider the consent form. All subjects will be reminded of the voluntary nature of study participation. Using the consent form to structure discussion, research personnel will explain the study, its potential benefits and risks, and alternatives, and document the consent process by signature of the subject and the person obtaining consent. During informed consent procedures, individuals will be told about possible risks and benefits of participation. This will include information that questions asked may cause them to feel uncomfortable or upset. They will be informed that: they may withdraw from an assessment at any time for any reason and receive full reimbursement for that assessment; and, they may withdraw from the research study at any time without negative consequences. Subjects are further informed that we will perform an immediate evaluation of their dangerousness towards self or others should safety concerns arise during

assessments or treatment sessions. As well, they will be informed that we may contact their primary care physicians should concerns arise about medical or psychological risk.

3. Subject Comprehension and Capacity to Consent: The staff will assess the participant's understanding of the study using an IRB-approved adapted version of the San Diego Brief Assessment of Capacity to Consent (UBACC), that we have implemented successfully in all of our studies with older adults. If a participant fails to answer all questions correctly, the staff will re-explain the study and then test the participant again. At follow-up assessments, study staff will review relevant parts of the consent form with subjects and will remind subjects that their participation is voluntary and that they can withdraw at any time for any reasons.

4. Debriefing Procedures: At the final interview, the CRC will answer any questions subjects have about the study. Given the lack of deception, more formal debriefing procedures are not indicated.

5. Consent Forms: See attached.

6. Documentation of Consent: Consents will be stored within REDCap, and a copy will be e-mailed to the subject.

7. Costs to the Subject: There are no costs to the subject. Parking at URMC will be paid for by the study.

8. Payment for Participation: Participants will be paid \$60 for an internet-based/phone/Zoom survey follow-up at 3 months and \$30 for an internet-based/phone follow-up at 6 months.

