H3b: We will measure a behavioral indicator of connectedness (quality and quantity of positive social interactions), a psychological indicator of connectedness (loneliness), and indicators of well-being over the course of treatment and at 6-month follow-up to estimate the length of treatment needed for improvement; to estimate the proportion of participants who respond to treatment; and the proportion who maintain gains after treatment (to inform a fully powered, randomized efficacy trial).

II. CHARACTERISTICS OF THE RESEARCH POPULATION

a) Number of Subjects: We will enroll approximately =30 participants, anticipating n=24 will begin the intervention (considering exclusion criteria, interest in the intervention) and n=20 participants will provide follow-up data and complete a full course of Social Engage. Subjects will be caregivers (age 50 or older) for a community-dwelling family member with ADRD, living with (or in close proximity to) the family member with dementia. They will be recruited from the IRB approved Health Aging Research Program (HARP) Population Study (RSRB00068059) (see III-d Recruitment Procedures) and Research Match.

b) Gender, Age, Racial, and Ethnic Origin of Subjects:

Women will be well-represented in this study. Caregivers in the US are more likely to be women (67%); Caregivers are also more likely to be white, non-Hispanic (67%), while 10% are African American and 8% are Hispanic. Using the 2018 Alzheimer's Disease Facts and Figures along with our local demographic distributions, we plan to target 25% minority and 67% women enrollment. We will proactively recruit minority participants (including targeting men for enrollment, as they represent the gender minority in the caregiver population) using best practices for minority recruitment, including working with providers serving minorities; collaborating with community gatekeepers; tailoring the recruitment materials to the culture and education level in inner city populations.

Our planned recruitment is as follows:

Racial Categories	Ethnic Categories				Total	
	Not Hispanic or Latino		Hispanic or Latino			
	Female	Male	Female	Male		
American Indian/ Alaska Native	0	0	0	0	0	
Asian	0	0	0	0	0	
Native Hawaiian or Other Pacific Islander	0	0	0	0	0	
Black or African American	4	1	0	0	5	
White	13	9	2	0	24	
More than One Race	1	0	0	0	1	
Total	18	10	2	0	30	

c) Inclusion Criteria (assessed at the HARP screening assessment):

1. Age \geq 50 yrs;
2. English speaking;

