3. Caregiver for a community-dwelling family member with ADRD, living with (or in close proximity to) family member with dementia;

4. Endorse elevated caregiving distress as measured by a score of greater than 11 on the 10-item Perceived Stress Scale (PSS-10) and/or a score of 5 or greater on the Modified Caregiver Strain Index (MCSI);
5. Endorse clinically significant loneliness as measured by a score of greater than 6 on the UCLA Loneliness Scale: Short Form.
6. Has access to e-mail in order to complete the e-consent module in REDCap which will be used in this study.

d) Exclusion Criteria (assessed at the HARP screening assessment):

1. Primary language is not English;
2. Recent or current psychosis;
3. Significant cognitive impairment on a cognitive screening measure at the HARP screening assessment;
4. Hearing problems that preclude completion of the intervention.

e) Vulnerable Subjects: Individuals who are 50 years of age and older with social risk factors for poor mental and physical health outcomes will be included. The results of this study will inform future research and clinical interventions aimed at improving mental health treatment for older caregivers.

III. METHODS AND PROCEDURES

a) Design: This study is a single-arm clinical trial of Social Engage psychotherapy. We will enroll n=30 participants. Participants will complete up to 8 weekly individual Social Engage psychotherapy sessions by Zoom. Participants will be allotted up to 3 months to complete all sessions, a time-frame that allows for two weeks without meeting to address life stressors such as illnesses that may pop up. The first and last session are longer – up to 60 minutes if needed. Middle sessions are shorter (20-45 minutes). Participants will complete follow-up assessments at 3-months (phone/Zoom and online via REDCap) and 6-months (online via REDCap or by phone).

The study team will remain vigilant about any further changes that need to be made to study procedures if there are changes to the research reboot guidance found here:

<https://www.urmc.rochester.edu/coronavirus/coronavirus-research/guidance-for-researchers/human-subjects-research.aspx>

b) Intervention Setting: The assessments and intervention will be remote by phone/Zoom/online.

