c) Recruitment Setting and Procedures: Subjects will be recruited via the IRB approved HARP Population Study (RSRB00068059), a research registry run by the current study's Investigators. In compliance with procedures of the Population Study protocol, subjects of the Population Study consent to allow HARP Population Study researchers to share subjects' identifiable data (both name and contact information) with investigators conducting HARP research at the University of Rochester; in addition, they consent to allow their data collected as part of the Population Study to be included in their research record for subsequent HARP studies they participate in, including the current study. All eligible participants will be given information about this study at their HARP in-person assessment. Contact information is collected and maintained via the IRB approved HARP Database Study. A brochure describing the study will be given to participants in the HARP Population study (brochure is uploaded in the rsrb online application). Information about the study will also be posted on the PI's URMC lab webpage (content to be displayed is uploaded in the rsrb online application) and the URMC Clinical Trials website. Information about this study will also be provided in the ResearchMatch registry. We will utilize a REDCap eligibility screening survey given the relatively low base rate of loneliness, which is our key inclusion criteria, to increase the efficiency of our screening/enrollment process. Information about the study will be provided at the beginning of the survey. Individuals who complete this survey and endorse loneliness (UCLA Loneliness Scale) and at least mild stress will have the option to provide their contact information to share with the Healthy Aging Research Program (HARP) staff to complete the HARP Database (RSRB00067245) and Population Study (RSRB00068059) assessments, which will provide information needed to determine final eligibility for this Engage Coaching study, which is

part of the Rochester Roybal Center for Social Ties & Aging Research. The link to the eligibility screen will be available via research match, the URMC Clinical Trials website, and the URMC website with information about the study.

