e) Assessment Measures & Administration Schedule: All baseline measures will be administered as part of screening through the HARP studies (described above). The following list specifies the assessment measures we propose to collect at follow-up assessments, with assessments conducted at both 3 and 6 month follow-up unless otherwise specified:

Domain 1, Social connectedness: Loneliness scales (UCLA Loneliness Scale and DeJong Loneliness Scale); Berkman-Syme Social Network, Unidimensional Relationship Closeness Scale, *PROMIS social functioning* computerized adaptive tests (satisfaction with roles/activities, social isolation, meaning/purpose, companionship, emotional support, instrumental support).

Domain 2, Caregiving: *Montgomery Borgatta Caregiver Burden Scale*, Modified Caregiver Strain Index (MCSI), Caregiver Reaction Scale

Domain 3, Health indicators: WHODAS, PROMIS computerized adaptive tests of depression, anxiety, fatigue and pain interference; Modified Cornell Services Index (only 3 month); Neuropsychiatric Inventory (only 3 month), FAST (only 3 month) Modified Barthel Index (only 3 month), Columbia Suicide Severity Rating Scale (only 3-month).

Domain 4, Well-being indicators: WHOQOL-BREF is a 36-item measure of several domains of health related quality of life

Domain 5, Mechanisms of behavior/social connectedness change. *Interpersonal Needs Questionnaire (INQ)*; the PSS-10 measures perceived stress.

Domain 6, Feedback about intervention

Participations will be provided an opportunity to discuss what they liked and did not like about the intervention, including what aspects they found helpful. This part of the 3 month interview will be recorded on Zoom. A short self-administered feedback questionnaire will be completed at 6 month follow-up.

f) Study Conditions: This study is a single-arm clinical trial of Social Engage psychotherapy. [name] conducted a study at URMC (K23MH096936) using Social Engage psychotherapy that demonstrated increases in well-being and social engagement for lonely older adults. Social Engage psychotherapy involves psychoeducation on the importance of social connections for health as well as structured goal setting for increasing social

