Aim 3 is to obtain evidence for a signal for efficacy with regards to social connectedness. Baseline data from the assessment battery will be used: a behavioral indicator of social connectedness (quality and quantity of positive social interactions), a psychological indicator of connectedness (loneliness), mechanisms of change (autonomy, competence, and relatedness), and indicators of well-being (psychological distress and quality of life). Assessments will be completed at the end of intervention (3 months), and 6-month follow-up. Follow-up data will be used to estimate the length of treatment needed to demonstrate improvement and to estimate the proportion of participants who demonstrate increases in social connectedness by the end of the intervention and the proportion who maintain gains after the intervention. Our hypotheses will be tested with repeated measures ANOVAs with the Stata software package; significant increases support a signal for efficacy.

h) Data and Safety Monitoring Plan: See Data and Safety Monitoring Plan document.

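### If Aim 3 loneliness is scored on the UCLA form used for entry, the baseline is the selecting score, so regression to the mean alone can produce an efficacy signal in this single-arm trial

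*Protocol*

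**What the plan says.** - **Entry.** Protocol II.c is headed "Inclusion Criteria (assessed at the HARP screening assessment". Criterion 5 reads "Endorse clinically significant loneliness as measured by a score of greater than 6 on the UCLA Loneliness Scale: Short Form".
- **Earlier filter.** For people arriving through the online REDCap survey, Protocol III.c passes on those described as "Individuals who complete this survey and endorse loneliness (UCLA Loneliness Scale) and at least mild stress". The HARP assessments then settle eligibility. The same section calls the base rate of loneliness relatively low.
- **Baseline.** Protocol III.e: "All baseline measures will be administered as part of screening through the HARP studies". No later baseline, taken once eligibility is known, is described. The SAP (June 2019) takes baseline from the STAR core battery without saying when it is given. The protocol (December 2020) is the later document, and it ties baseline to screening.
- **Outcome.** At 3 and 6 months, Protocol III.e, Domain 1 lists "Loneliness scales (UCLA Loneliness Scale and DeJong Loneliness Scale". In III.g, the Aim 3 outcome is only "a psychological indicator of connectedness (loneliness", with no scale named.
- **Design and decision rule.** Protocol III.a: "This study is a single-arm clinical trial of Social Engage psychotherapy". Protocol III.g tests Aim 3 by repeated measures ANOVA and adds that "significant increases support a signal for efficacy". For loneliness, improvement is a fall in the score.
- **Use.** Hypothesis H3b and the SAP also plan to estimate the proportions who respond and who keep their gains, for planning a randomised trial.

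**The concern.** A questionnaire score is a stable level plus a part that varies from day to day. People admitted because one score was high have, on average, a positive transient part on that occasion. At the next measurement it has faded, and the group mean drops even if nothing was done. When the admitting score is also the baseline, the whole drop counts as change from baseline. A control arm would show the same drop and cancel it, but this trial has none.

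The stake is limited to Aim 3. A significant fall in loneliness could be taken as promise of efficacy when there is none. The proportions who respond and who maintain gains would be too high for the same reason, and the next trial would be planned on them. Aims 1 and 2 are unaffected. Outcomes not used for entry are affected only through their correlation with the entry score. PSS-10 and MCSI are affected little, because a high score on either one is enough.

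**Working it through.** **The plan's own figure.** The SAP expects 24 to start, with 20% attrition (15% thought more likely): 24 × 0.80 = 19.2 and 24 × 0.85 = 20.4. This agrees with the stated n=20. The documents give no alpha, effect size, SD or reliability.

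**Inputs.**
- From the documents: n=20; baseline, 3 and 6 months (the SAP's 1-month assessment is absent from the later protocol); repeated measures ANOVA; selection above a cut at screening.
- Assumed: two-sided alpha 0.05; reliability r from 0.70 to 0.90; share passing the cut p from 10% to 50%; same form at entry and follow-up; no treatment effect.

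**Expected fall.** Give the score variance 1, made up of a true score (variance r) and a transient part (variance 1 − r) that is independent between occasions. Selecting those above cut c, with pass rate p, gives

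expected fall = (1 − r) × φ(c) / p, in SD units.

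- r=0.70, p=10%: 0.30 × 1.755 = 0.53
- r=0.80, p=20%: 0.20 × 1.400 = 0.28
- r=0.85, p=30%: 0.15 × 1.159 = 0.17
- r=0.90, p=50%: 0.10 × 0.798 = 0.08

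**How often the test is significant.** The simulation used 20,000 null trials per cell. The F test has 3 − 1 = 2 and 19 × 2 = 38 degrees of freedom. "Twice" in the table means that an independent survey score also had to pass the same cut. Response is illustrated as a fall of at least 0.5 SD at 3 months, because the documents define no threshold.

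| r, share passing | Fall, once / twice (SD) | Significant, once / twice | Null responders, once / twice / re-measured |
|---|---|---|---|
| 0.70, 10% | 0.53 / 0.33 | 91% / 52% | 51% / 40% / 26% |
| 0.80, 20% | 0.28 / 0.17 | 52% / 21% | 36% / 29% / 22% |
| 0.85, 30% | 0.17 / 0.10 | 28% / 12% | 27% / 22% / 18% |
| 0.90, 50% | 0.08 / 0.05 | 11% / 7% | 17% / 15% / 13% |

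Nearly all the significant results are falls. With a baseline re-measured after eligibility, the rate in these eight cells is 4.7% to 5.3%. Null response still met at 6 months is 7% to 33% (once) or 6% to 23% (twice), against 5% to 13% re-measured.

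**Sensitivity.**
- *Wider reliability range (0.5 to 0.9), counting only significant falls* (nominal 2.5%): 11% to 99.5% selected once, 6% to 89% selected twice, and 2.3% to 2.6% with a fresh baseline.
- *Coarse scores* (0.5 SD steps, capped at −1.5 and +2 SD): 18% to 98% once, 9% to 73% twice, about 5% re-measured.
- *A different loneliness scale as outcome* (same reliability, true-score correlation 0.8, selected once): about 5% if it shares no same-day transient part with the entry form; 7% to 31% if those parts correlate 0.5.
- *Slow states.* Suppose half to two-thirds of the transient variance is a state that correlates 0.5 to 0.8 with the repeat and is gone by 3 months. The repeat baseline then gives about 5% to 37%, against 8% to 91% with the screening baseline.

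**The case against.** The strongest reply is that the premise is not in the text. Entry uses the Short Form, follow-up lists a UCLA scale without naming the version, and Aim 3 says only loneliness. On a different scale the inflation may be nil. This stands, and it is why the point is conditional. It also shows that the plan needs to name its scale.

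A second reply is that no sentence says one UCLA administration serves both purposes. The HARP studies are plural, and Protocol IV.3 mentions a two-hour baseline interview. But neither that interview nor the STAR core battery is described as a separate assessment after eligibility is settled, and III.e places every baseline measure within screening.

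Third, the size is very uncertain. The 91% cell combines a 10% pass rate with single selection, whereas the survey was added because loneliness is uncommon. For survey recruits the twice-selected figures apply, at most 52% and 12% to 21% in the middle cells. The mix of recruitment routes is unknown. This stands too, and the upper end should not be read as an estimate.

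Finally, this is Stage One work with several Aim 3 indicators, and efficacy would be decided under randomisation. That limits the harm but does not remove it, because the response proportions are meant to feed that later trial.

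**Conclusion.** The concern holds as a conditional one. If Aim 3 loneliness is scored on the entry form, its baseline is the selecting score, and a significant fall can arise with no treatment effect. Under the assumptions above, the null rate is about 11% to 91% selected once and 7% to 52% selected twice, against 5%. Every independent-error cell with the screening baseline exceeds 5%, though the mildest only slightly. The size depends on reliability, pass rate and recruitment mix, none of which the documents give. The point should be addressed because it bears on what Aim 3 can tell the next trial and costs little to correct. It does not undermine the feasibility aims.

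**What to change.** Use the HARP UCLA score for eligibility only. Repeat the same form once by REDCap after consent and before session 1; the SAP projects 1-2 weeks between enrolment and therapy, and the protocol should restate that window. Use the repeat as the Aim 3 loneliness baseline without re-applying the cut. State that one named UCLA version is used at entry, baseline, 3 and 6 months. Report change, response and maintenance as uncontrolled: the repeat removes regression due to independent error, only reduces the part due to states lasting weeks, and does nothing about natural improvement.

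The cost is one short form per participant and some wording in both documents. The apparent improvement and response proportion will probably be smaller. Some repeat baselines will lie at or below the entry cut: 14% to 53% of participants selected once and 8% to 36% selected twice, in the independent-error model. That is regression to the mean made visible, but the definition of response should say how these participants are handled.

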Engage Psychotherapy to Promote Connectedness in Caregivers

NCT04176601

Statistical Analysis Plan

6/30/2019

P30AG064103-Pilot2

Statistical Design & Power: Study 2

We will enroll n=30 participants, anticipating n=24 will begin the intervention (considering exclusion criteria, interest in the intervention) and a conservative potential attrition rate of 20% (15% is more likely based on the PIs' prior studies). Based on our prior RCT of Engage—including its flexible structure (e.g., accommodating phone sessions when needed) and high acceptability—we expect most participants will complete a full course of Social Engage (i.e., at least 6 sessions out of 8 allowed; we had 88% achieve this in our prior Engage study). We have also successfully retained caregivers in our intervention research. For [name] clinical trials, one of which includes an 8-week home-based computer intervention, and the other a 9-session in-person mindfulness group training (i.e., requiring attendance at a local community site), attrition rate continues to be very low, ~10%. Given these considerations, we anticipate n=20 participants will provide follow-up data and complete a full course of Social Engage. This calculation includes our expected recruitment rate (n=4 per month), projections about the length of time between enrollment and commencement of therapy (1-2 weeks), amount of time to complete the intervention (maximum of 3 months, including two weeks buffer for missed sessions), and time to complete follow-up assessments. Given start-up and time for data analysis, our study resources and recruitment infrastructure will support running our participants through all study procedures within the 1-year timeline.

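### Eligibility and all baselines come from the HARP assessment, with no stated maximum age and no repeat before therapy, so change before session 1 can enter the Aim 3 result

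*Protocol*

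**What the plan says.** The entry criteria are headed "Inclusion Criteria (assessed at the HARP screening assessment" and "Exclusion Criteria (assessed at the HARP screening assessment" (Protocol II.c and II.d). They include loneliness, worded as "Endorse clinically significant loneliness as measured by a score of greater than 6 on the UCLA Loneliness Scale: Short Form", and caregiving distress, defined as "a score of greater than 11 on the 10-item Perceived Stress Scale (PSS-10) and/or a score of 5 or greater"; the second of these scores is the MCSI (Modified Caregiver Strain Index). They also require that the family member lives in the community. Section III.e then states: "All baseline measures will be administered as part of screening through the HARP studies (described above".

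The source of participants is the HARP Population Study, a standing registry. Its members "consent to allow their data collected as part of the Population Study to be included in their research record for subsequent HARP studies" (III.c, repeated in VII.1).

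The only interval given before therapy is in the SAP (Statistical Design & Power), which refers to "projections about the length of time between enrollment and commencement of therapy (1-2 weeks". It is a projection, and its clock starts at enrollment.

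Aim 3 measures change in connectedness and well-being in one arm by repeated measures ANOVA, and reads a significant increase as a signal of efficacy (Protocol III.g).

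**The concern.** Loneliness, stress, strain and the care setting are current states, and a score from some time ago may not describe the caregiver who starts therapy. If it does not, two things follow. The caregiver may be outside the target population when treated. And the old score becomes the Aim 3 baseline, so whatever changed between the HARP assessment and session 1 is counted in the change to 3 months.

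There is no control arm to show that change separately. Protocol IV.9 documents outside services over the 6 months of follow-up, but nothing provides for services used between the HARP assessment and consent. The response and maintenance proportions are meant to inform a randomized trial, so an error here would carry forward. If no pre-therapy measurement is taken, analysts cannot recover it later.

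**Working it through.** **The plan's own figure.** The SAP expects 24 people to start therapy, with attrition of 20% (conservative) or 15% (more likely). 24 × 0.80 = 19.2 and 24 × 0.85 = 20.4, which agrees with its 20 completers. It states no effect size, SD or alpha.

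**What is bounded, in time order.**
- HARP assessment to consent: no limit stated.
- Consent: identity, comprehension and capacity checks only (Protocol IV.4, VII.2, VII.3). No entry scale is repeated.
- Enrollment to session 1: 1-2 weeks, projected (SAP).
- Session 1: social history and a first action plan (Figure 1). No outcome scale is scheduled.
- Session 1 to end of therapy: up to 3 months (III.a).
- Payments are listed for 3 and 6 months only (VII.8), which fits there being no study-run baseline. The two-hour baseline interview in IV.3 is, given III.e, most naturally the HARP interview.

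**Share of elapsed time that is treatment.** Let m be the age in months of the HARP assessment at enrollment (assumed). Take 0.5 month to session 1 and a full 3-month course. Share = 3/(m + 0.5 + 3):
- m = 0: 3/3.5 = 86%
- m = 3: 3/6.5 = 46%
- m = 6: 3/9.5 = 32%
- m = 12: 3/15.5 = 19%

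This describes calendar time. It gives neither the size nor the direction of any change.

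**Response proportion.** Among 20 completers, each misclassified person moves it by 1/20 = 5 points.

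**Illustration of how an ageing score could act.** Every input here is assumed, because the documents give none: normal scores, reliability 0.9, true-score correlation 0.95 from consent to 3 months and ρ from HARP to consent, a share p of people above the cut-off, no treatment effect, no population trend, and a paired t-test at n = 20 with two-sided alpha 0.05 (nominal 2.5% in the direction of improvement). The t-test stands in for a two-time ANOVA.

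Expected fall with the HARP score as baseline = (1 − r) × φ(t)/p, where t is the cut-off in SD units, φ the standard normal density, and r = 0.9 × ρ × 0.95.
- p = 0.20, φ(t)/p = 1.40. At ρ = 1, r = 0.855 and the fall is 0.145 × 1.40 = 0.20 SD. At ρ = 0.7, r = 0.5985 and the fall is 0.4015 × 1.40 = 0.56 SD.
- p = 0.40, φ(t)/p = 0.966. The falls are 0.145 × 0.966 = 0.14 SD and 0.4015 × 0.966 = 0.39 SD.

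Simulated rate of a false significant improvement (%):

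| ρ | HARP score as baseline, p=0.20 / 0.40 | Fresh baseline not used for selection, p=0.20 / 0.40 | Fresh score both re-checks eligibility and is baseline, p=0.20 / 0.40 |
|---|---|---|---|
| 1.00 | 38.0 / 20.3 | 7.0 / 5.4 | 23.7 / 13.7 |
| 0.95 | 47.4 / 25.5 | 6.9 / 5.1 | 23.2 / 13.7 |
| 0.90 | 56.1 / 30.6 | 6.6 / 4.9 | 24.8 / 14.2 |
| 0.80 | 71.8 / 40.3 | 6.2 / 4.7 | 25.7 / 15.3 |
| 0.70 | 82.7 / 51.3 | 5.1 / 4.2 | 26.5 / 15.4 |

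The ρ = 1 row has no ageing, so its 38.0% and 20.3% come from selecting on a high score. Only the rise down the first results column belongs to this point: at most 82.7 − 38.0 = 44.7 points, or 51.3 − 20.3 = 31.0 points, over the assumed range of ρ. The other columns bear on the choice of fix.

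**The case against.** The strongest reply is that the plan treats the HARP assessment as its own prospective screening visit. Section III.c says eligible people learn of the study at that assessment. Web and ResearchMatch recruits take a pre-screen first and complete the HARP assessments afterwards. Some criteria are specific to this study, such as e-mail access for e-consent and hearing adequate for the intervention, and an old registry visit would not naturally have recorded them. Nothing says archived scores will be searched, and the carry-over clause is a data-sharing permission. A reassessment schedule might also sit in the separate Population Study protocol.

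Much of this stands. Many gaps may be short, and the limit is best described as not stated in these documents. A reader might infer that the plan positively admits anyone who qualified many months ago; that goes too far, because it rests on silence. But none of these sentences is a time rule, VII.1 describes handing out the brochure without tying it to the assessment, and III.c lets investigators receive registrants' contact details.

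It is also fair to say that this is a Stage One study and that a single arm cannot attribute change to therapy even with a same-day baseline. That limits what is at stake, but it does not make a baseline of unknown age as good as one taken just before therapy.

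**Conclusion.** The point holds as a gap in the stated method that should be closed before enrollment. Eligibility and baseline rest on an assessment of unstated maximum age, with no repeat before session 1, and Aim 3 has no comparison group to separate out earlier change. The size is unknown, because it depends on a gap the documents do not give.

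Three stronger readings are not supported:
- That old scores would inflate the apparent benefit. Loneliness or strain may worsen before session 1, which would hide benefit. The simulation shows inflation only because it assumes selection on a high score and no population trend.
- That the time shares, or the full false-improvement rates, measure this bias. The first are calendar arithmetic with m assumed, and the second include regression to the mean that is present at ρ = 1.
- That the protocol itself calls the entry measures dynamic. In the Background that word describes barriers to connectedness.

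Aim 1 completion and the Aim 2 strategy counts use no baseline score, though out-of-date eligibility could affect who is in them.

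**What to change.** - **III.e:** have every participant complete the Aim 3 connectedness and well-being scales by REDCap or phone after consent and before session 1, and use these values, which play no part in selection, as the Aim 3 baseline. Doing this for everyone avoids mixing two kinds of baseline among about 20 completers.
- **II.c:** state a maximum age for the HARP assessment (for example 30 days, which is a judgment). Beyond it, repeat the UCLA Short Form, PSS-10 and MCSI and reconfirm that the family member still lives in the community. Keep this measurement separate from the Aim 3 baseline; one score serving both purposes leaves regression to the mean, as the last column of the table shows.
- **Reporting:** give each participant's HARP-to-session-1 interval.

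Under the assumed inputs, a fresh baseline with eligibility still set at HARP brings the false-improvement rate to about 4-7%, still above the nominal 2.5%. The combination with a separate re-check was not simulated. The cost is one short extra questionnaire set per participant, and a few people may no longer qualify. The planned sample size and the single-arm design do not change.
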